#### C.4.8 Assessments done at discharge (both SAVR and TAVI)

Prior to hospital discharge (or within 7 days post-index procedure, whichever occurs first) the following tests and procedures must be performed and data collected:

- Physical Examination
  - Vital signs
  - Major system findings
  - Skin Assessment – refer to Radiation Exposure and Data Collection, **Appendix R.23**
- Concomitant Medications
  - Use of relevant medications (diuretics, aspirin, anticoagulants, ACE-I, ARB, beta-blockers, statins and anti-platelets)
- Routine Laboratory Tests:
  - Complete Blood Count:
    - White Blood Count
    - Hematocrit
    - Hemoglobin
    - Platelet Count
  - Creatinine and Creatinine Clearance
  - Cardiac Enzymes (CK/CK-MB)
  - International Normalized Ratio (INR), if applicable
  - Activated Partial Thromboplastin Time (aPTT)
  - B-type Natriuretic Peptide (BNP) or NT-proBNP
  - Liver Panel:
    - ALT
    - AST
    - Albumin
  - Sodium
  - Potassium
- Neurological Assessments
  - National Institute of Health Stroke Scale (NIHSS)
  - Modified Rankin Score (mRS)
  - Mini-Mental State Exam (MMSE-2:SV)
  - Additional Neurological testing:
    - Visual Fields Testing
    - Gait Assessment
    - Hand Function
    - Writing Evaluation
    - Drawing Assessment
- Transthoracic Echocardiogram (TTE)
  - Comprehensive transthoracic 2D echocardiogram (TTE) should be performed at least 24hours post-procedure but prior to discharge to assess device success (and no later than 7 days, whichever comes first)
  - Echocardiograms will be performed according to Echocardiography Procedures found in **Appendix R.7**
- 12-lead Electrocardiogram
- Adverse Event review

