12. Echocardiographic assessment of prosthetic valve performance at discharge, 6 months, 12 months, 24 months, and annually thereafter up to 5 years using the following measures:

- transvalvular mean gradient
- effective orifice area
- degree of prosthetic aortic valve regurgitation (including transvalvular and paravalvular)

The four echocardiographic measurements will be evaluated at discharge, 6 months, 12 months, 24 months, and annually thereafter up to 5 years. All implanted subjects undergoing echocardiography procedures will be evaluated.

Continuous measures will be evaluated using a Bayesian version of a two-sample t-test. Categorical variables will be evaluated using Bayesian version of a comparison of polytomous outcomes.

Additionally, incidence of moderate/severe aortic insufficiency at discharge will be compared between groups using the Bayesian version of a comparison of proportions.

13. Aortic valve disease related hospitalizations

The number of subjects re-hospitalized after the initial index procedure will be compared at 30 days, 6 months, 12 months, 18 months, 24 months, and annually thereafter up to 5 years.

Incidence of recurrent hospitalization will be provided at 30 days, 6 months, 12 months, 18 months, 24 months, and annually thereafter up to 5 years. The statistical method will be the Bayesian version of a comparison of proportions (with predictions).

14. Cardiovascular deaths and valve-related deaths

The number of subjects experiencing cardiovascular deaths and valve-related deaths at 30 days, 6 months, 12 months, 18 months, 24 months, and annually thereafter up to 5 years. Incidences will be compared between groups. The statistical method will be the Bayesian version of a comparison of proportions (with predictions).

15. Strokes and TIAs

The number of subjects with strokes (of any severity) and TIAs at 30 days, 6 months, 12 months, 18 months, 24 months, and annually thereafter up to 5 years. A separate analysis will be performed for each of the following:

- a composite of all strokes and TIAs
- disabling strokes only
- non-disabling strokes only
- TIAs only

The statistical method will be the Bayesian version of a comparison of proportions (with predictions).

Additionally, incidence of all strokes at 30 days or hospital discharge, whichever is longer, will be compared between groups using the Bayesian version of a comparison of proportions.

16. Peri-procedural Neurological Injury (Stroke, TIA, Encephalopathy)

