For each treatment group, the proportion of subjects with a neurologic injury (stroke, TIA, or encephalopathy) at discharge or at 7 days post-index procedure (whichever occurs first) will be calculated. The numerator will be the number of subjects with a neurologic injury (stroke, TIA, or encephalopathy) at discharge or at 7 days post-index procedure (whichever occurs first), and the denominator will be the number of subjects in that treatment group. Results will also be presented separately for disabling stroke, non-disabling stroke, TIA, and encephalopathy. Proportions will be compared between groups using Bayesian version of a comparison of proportions.

17. Index procedure related MAEs

Index procedure-related MAE events will be summarized and event rates will be provided at 30 days. The numerator will be the number of procedure-related MAE events experienced by the end of the 30-day follow-up visit, and the denominator will be the number of subjects evaluated at the 30-day follow-up visit (or a later follow-up) plus the number of subjects not evaluated but who experienced a procedure-related MAE event prior to the end of the follow-up visit window.

The endpoint is descriptive and no statistical hypothesis test will be performed.

18. Length of index procedure hospital stay

The length of TAVI or SAVR hospital stay will be summarized for all subjects undergoing a trial procedure.

The endpoint will be evaluated between groups using a Bayesian version of a t-test.

19. Presence of atrial fibrillation at post-procedure, discharge, 30 days, 6 months, 12 months, 18 months, 24 months, and annually thereafter up to 5 years.

The statistical method will be the Bayesian version of a comparison of proportions (with predictions).

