where  $\mu_{TAVI}$  and  $\mu_{SAVR}$  denote the mean improvements in the KCCQ score from baseline to 30 days. For subjects with KCCQ score at both baseline and 30 days, the improvement in KCCQ will be calculated as  $KCCQ_{30day} - KCCQ_{baseline}$ . This objective will be evaluated using a Bayesian version of a two-sample t-test (see Section C.11). The posterior probability  $P(H | data)$  will be calculated and compared to a threshold of 0.95.

5. Length of index procedure hospital stay after TAVI vs. SAVR (secondary objective #18). The hypothesis of interest is

$$H: \mu_{TAVI} < \mu_{SAVR}$$

where  $\mu_{TAVI}$  and  $\mu_{SAVR}$  denote the mean length of index hospital stay. This objective will be evaluated using a Bayesian version of a two-sample t-test (see Section C.11). The posterior probability  $P(H | data)$  will be calculated and compared to a threshold of 0.975.

6. Transvalvular mean gradient at 12 months (superiority): TAVI vs. SAVR (secondary objective #12). The hypothesis of interest is

$$H: \mu_{TAVI} < \mu_{SAVR}$$

where  $\mu_{TAVI}$  and  $\mu_{SAVR}$  denote the average mean gradient from at 12 months, measured in mmHg. This objective will be evaluated using a Bayesian version of a two-sample t-test (see Section C.11). The posterior probability  $P(H | data)$  will be calculated and compared to a threshold of 0.975.

7. Effective orifice area at 12 months (superiority): TAVI vs. SAVR (secondary objective #12). The hypothesis of interest is

$$H: \mu_{TAVI} > \mu_{SAVR}$$

where  $\mu_{TAVI}$  and  $\mu_{SAVR}$  denote the mean effective orifice area at 12 months, measured in  $cm^2$ . This objective will be evaluated using a Bayesian version of a two-sample t-test (see Section C.11). The posterior probability  $P(H | data)$  will be calculated and compared to a threshold of 0.975.

8. Change in Kansas City Cardiomyopathy Questionnaire (KCCQ) score from baseline to 30 days (superiority): TAVI vs. SAVR (secondary objective #11). The hypothesis of interest is

$$H: \mu_{TAVI} > \mu_{SAVR}$$

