### **D.2 Potential Benefits**

Patients treated with TAVI may experience improvement in quality of life, morbidity and mortality compared to traditional open-heart aortic valve replacement. Potential benefits include, but are not limited to, absence of open-heart surgery-related risks, reduced procedure time, reduced anesthesia procedure time, shorter hospital stay and earlier return to normal activities than after open-heart aortic valve replacement.

There is no direct benefit associated to participation in this trial, but the information obtained during this trial will be used scientifically. The results of this trial can help physicians understand the implications of transcatheter treatment of patients with intermediate risk for surgery.

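### Secondary endpoint #16 assesses peri-procedural neurological injury at discharge or day 7, whichever is first, so the arms are compared over different lengths of time if one goes home earlier

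*Combined protocol and SAP*

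**What the plan says.** C.6.8.1 #16 takes as its numerator the subjects with stroke, TIA or encephalopathy, and the proportion "at discharge or at 7 days post-index procedure (whichever occurs first) will be calculated". For the proportion, "the denominator will be the number of subjects in that treatment group". The result is inferential: "Proportions will be compared between groups using Bayesian version of a comparison of proportions". The next endpoint, #17, is labeled descriptive; #16 is not, and C.6.7.2 lists it among the secondary endpoints with inferential statistics. Results are also presented separately for disabling stroke, non-disabling stroke, TIA and encephalopathy.

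The examination that feeds the endpoint follows the same clock. C.4.8 has "Prior to hospital discharge (or within 7 days post-index procedure, whichever occurs first) the following tests and procedures must be performed", and these include the neurological assessments.

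On length of stay, D.2 lists among the potential benefits of TAVI a "shorter hospital stay and earlier return to normal activities than after open-heart aortic valve replacement". C.6.10.1 makes a shorter mean index stay with TAVI the first superiority test in the labeling sequence (item 5).

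Other early event comparisons do not close at the earlier date. Under #15, "incidence of all strokes at 30 days or hospital discharge, whichever is longer, will be compared between groups". MACCE, major vascular complications and major or life-threatening bleeding are handled in the same way.

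**The concern.** Discharge happens after randomization and may depend on the treatment given. A window that ends at each subject's own discharge is then itself an outcome of treatment. If TAVI subjects leave on day 4 and SAVR subjects stay to day 7, a TAVI subject with an onset on day 5 is outside the window and a SAVR subject with the same onset is inside it. Both are in the denominator, so the unobserved TAVI days are scored as event-free.

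At stake is a between-arm difference in neurological injury, and in its four component results, that reflects length of stay rather than neurological risk. Encephalopathy matters most. O.2 defines it broadly, with delirium and confusion among the examples. It is not in #15 and not in the MAE list (C.5.1.4), so in the text reviewed #16 is its only between-arm comparison.

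**Working it through.** The plan gives no event rate, length of stay or success threshold for #16, so there is no figure to reproduce. The check asks what the window alone can do when the arms are truly equal.

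From the documents:
- Window, denominator and comparison of proportions: C.6.8.1 #16.
- 800 per arm: 1600 mITT subjects at 1:1 (C.6.5.2).
- Beta(1,1) priors: stated for the primary analysis in C.6.5.2 and borrowed here.
- Threshold 0.975: borrowed from the superiority tests in C.6.10.1.

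Assumed, not in the documents:
- Cumulative counting of new events.
- The same true 7-day risk R = 5% in both arms.
- All TAVI subjects discharged on day 4; all SAVR subjects observed to day 7 (or day 6 in one case).
- A share s of the 7-day onsets falls by day 2 and the rest is spread evenly to day 7, so the share captured by day t is F(t) = s + (1 − s)(t − 2)/5. With a constant hazard, the captured risk is 1 − (1 − R)^(t/7).

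Worked case, s = 0.70:
- F(4) = 0.70 + 0.30 × 2/5 = 0.82. The TAVI rate is 5% × 0.82 = 4.1%, against 5.0% for SAVR.
- The difference is 0.9 points. SE = √(0.041 × 0.959/800 + 0.050 × 0.950/800) = 1.04 points, so z = 0.86.
- The chance that the posterior probability of 'TAVI lower' exceeds 0.975 is about Φ(0.86 − 1.96) = Φ(−1.10) ≈ 14%. Simulation (200,000 trials, normal approximation to the two Beta posteriors) gives 13%.

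Simulated results at R = 5%, TAVI discharge on day 4:

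| Onset pattern | SAVR observed to | TAVI rate | SAVR rate | Ratio | Chance of false 'TAVI lower' |
|---|---|---|---|---|---|
| 85% by day 2 | day 7 | 4.55% | 5.0% | 0.91 | 6% |
| 70% by day 2 | day 7 | 4.1% | 5.0% | 0.82 | 13% |
| 50% by day 2 | day 7 | 3.5% | 5.0% | 0.70 | 31% |
| Constant hazard | day 7 | 2.9% | 5.0% | 0.58 | 58% |
| 70% by day 2 | day 6 | 4.1% | 4.7% | 0.87 | 8% |

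Sensitivity of the 70%-by-day-2, SAVR-to-day-7 case:
- True risk 3% or 10% instead of 5%: 9% or 24%.
- TAVI discharge on day 3 or day 5 instead of day 4: 21% or 8%.

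With one fixed 7-day window for everyone, the expected difference is zero and the chance is 2.3% to 2.5% at true risks of 3%, 5% and 10%.

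**The case against.** **The direction is not settled.** A reader might infer that #16 is bound to make TAVI look safer. The documents do not support that. The wording could mean injury present at the discharge or day-7 examination rather than events accumulated up to it. Earlier discharge would then leave less time for a transient deficit to resolve, and the tilt could run against TAVI. Including TIA, which by definition resolves, favors the cumulative reading but does not settle it. Under either reading the arms are assessed at different times.

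**Most of the content is covered elsewhere.** #15 compares strokes and TIAs together, disabling stroke, non-disabling stroke and TIA at a common 30 days. That covers three of the four components of #16, though not encephalopathy or the composite that includes it.

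**No claim rests on it.** A reader might infer that a labeling claim is inflated. C.6.10 places #16 outside the testing hierarchy and says that such objectives will not support claims. The stroke claim uses 30 days or discharge, whichever is longer.

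**The difference in stay is anticipated, not measured.** D.2 speaks of potential benefits and C.6.10.1 states a hypothesis. No length of stay is given, and both arms have the same guidance of at least 48 hours of temporary pacing (C.4.7). If nearly all onsets fall within 48 hours, the effect is small.

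**The SAP may say more.** C.6.5.2 defers further analysis detail to the SAP, whose handling of #16 is not in the part of the document available here.

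These points limit the consequence and the certainty about direction. They do not supply a common window for #16, and none was found in the text reviewed.

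**Conclusion.** The point holds as a moderate one. #16 compares arms over a window whose length can depend on treatment, with a denominator that ignores the difference. Under cumulative counting this favors the earlier-discharged arm; if injury still present at the visit is meant, the direction is open.

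The size is a wide range, not a single number: about 6% to 58% for a false 'TAVI lower' result in the SAVR-to-day-7 scenarios tabulated, and about 8% when SAVR also leaves early, on day 6. Every figure rests on assumed risk, onset timing and discharge days and on a borrowed threshold. A reader might take the upper end as the expected error rate, but the documents give no basis for choosing it. The practical loss is greatest for encephalopathy and for the composite.

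**What to change.** In C.6.8.1 #16, define the numerator as subjects with a new stroke, TIA or encephalopathy with onset from day 0 through day 7 after the index procedure, in both arms, regardless of discharge. Take events from the adverse-event records by onset date. Keep the discharge/day-7 count as a descriptive result. This also settles that counting is cumulative.

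The cost is one sentence in the protocol, any matching SAP text, and no new visit or test. C.5.2 already captures all new or worsening adverse events through the 24-month visit, and the 30-day visit includes an NIHSS and adverse-event review (C.4.9.1). The disabling-stroke component already needs the 90-day mRS (O.2), so the analysis cannot be closed at discharge in any case.

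The downside should be stated in the plan. After discharge, events rest on adverse-event reports rather than a neurologist's or stroke specialist's examination, in a trial whose assignment is not blinded (C.4.5). A 30-day NIHSS will not show a deficit that has resolved. Mild transient events may still be under-detected in the earlier-discharged arm, so the change reduces the tilt but may not remove it.

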### *C.5.2 Reporting*

Investigators are required to keep records on “all relevant observations, including records concerning adverse device effects (whether anticipated or unanticipated)” [21 CFR 812.140; ISO 14155 (2011)]. Adverse event collection will begin from the point of trial enrollment to trial closure. All new or worsening (from baseline) adverse events and technical observations will be captured on the AE eCRF through the 24-month follow-up visit. It is the responsibility of the Investigator to assess the subject for adverse events and capture the required adverse event information on the AE eCRF.

Once a subject has completed their 24-month scheduled follow-up visit only serious adverse events, major adverse events, cardiovascular events, device-related adverse events, including device related technical observations, unanticipated adverse device effects (UADE) or unanticipated serious adverse device effects (USADE), all strokes (CVAs) and deaths will be required to be reported. Reference section C.5.1 Adverse Events for event definitions and criteria. Medtronic representatives or their designees will conduct monitoring visits to review source documentation and verify the complete and accurate capturing of adverse events.

The Investigator must also notify the responsible IRB/MEC regarding new and significant safety information and any event identified by Medtronic that requires expedited FDA, and/or local regulatory agency, reporting as serious, unexpected, and related to the investigational device. It is the responsibility of the investigator to ensure site specific IRB/MEC safety reporting requirements are met.

Medtronic Clinical will ensure all device-related adverse events and all procedure-related SAEs are processed according to internal policies and procedures. When necessary, Medtronic Field Assurance will respond to sites in writing with the findings related to the product experiences.

The general procedure for investigators reporting any adverse event is as follows:

- Report the event to Medtronic as soon as possible but no later than the timeframes outlined below. (At the time of Site Initiation, sites will be provided with the telephone and other applicable contact information of the appropriate Medtronic designee).
- Complete all sections of the Adverse Event eCRF.
- Each unique event/diagnosis must be documented separately.

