##### C.6.7.2 Analysis of ITT and mITT Populations

For the subjects in the randomized population the primary analysis of the primary endpoint and inferential statistics for the following secondary endpoints will be performed on the ITT and mITT populations:

- Major adverse cardiovascular and cerebrovascular events (MACCE)
- Individual MACCE components
- Major adverse events (MAE)
- Conduction disturbance requiring permanent pacemaker implantation
- NYHA
- Six-minute walk test
- Ratio of days alive out of hospital versus total days alive
- Quality of life
- Echocardiographic assessment of valve performance
- Aortic valve disease-related hospitalizations
- Cardiovascular deaths and valve-related deaths
- Strokes and TIAs
- Per-procedural neurological injury
- Index procedure-related MAEs

- Length of index procedure hospital stay
- Device success
- Procedure success

C.6.7.3 Analysis of Implanted Population

The endpoints listed in C.6.7.2 will also be performed on the implanted population. Additionally, the implanted population will be used for analyzing the primary endpoint, secondary endpoint of prosthetic valve dysfunction, and echocardiographic assessment of valve performance.

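### Secondary endpoint 17 divides procedure-related MAE events by an outcome-dependent number of subjects, so its 30-day figure cannot be read as the percentage of subjects affected

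*Combined protocol and SAP*

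**What the plan says.** Protocol section C.6.8.1, endpoint 17, opens: "Index procedure-related MAE events will be summarized and event rates will be provided at 30 days". It then defines the ratio:

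- **Numerator.** "The numerator will be the number of procedure-related MAE events experienced by the end of the 30-day follow-up visit". The unit is the event.
- **Denominator.** Subjects evaluated at the 30-day visit or at any later one, "plus the number of subjects not evaluated but who experienced a procedure-related MAE event prior to the end of the follow-up visit window". The unit is the subject. An unevaluated subject with no event is left out.
- **Status.** "The endpoint is descriptive and no statistical hypothesis test will be performed".

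Section C.6.7.2 introduces a list with the statement that "inferential statistics for the following secondary endpoints will be performed on the ITT and mITT populations", and index procedure-related MAEs are on that list.

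Two neighbouring endpoints are built differently. Endpoint 16 (peri-procedural neurological injury) takes subjects with an injury over all subjects in the treatment group. Endpoint 3 gives the incidence of all MAEs at 30 days and later, analysed as a comparison of proportions.

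**The concern.** The numerator and denominator count different things. MAE (section C.5.1.4) is a list of components whose definitions in section O.2 overlap. A left ventricular perforation is named as a major vascular complication and also fits cardiac perforation. If it causes tamponade, that is a third component. Pericardial bleeding that needs pericardiocentesis is life-threatening bleeding, a fourth. Section C.5.2 adds: "Each unique event/diagnosis must be documented separately". One clinical episode can therefore enter the numerator several times.

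The denominator depends on the outcome, because having an event is what admits an unevaluated subject. That add-back is what a subject-level proportion needs to keep its numerator inside its denominator, and it does little for a mean number of events per subject. This suggests that a proportion was intended, but that is an inference. As written, the ratio is neither a clean proportion nor a clean mean count.

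What is at stake is how a reported safety figure is read. Section C.6.10.1 allows summary data from secondary objectives outside the hierarchy to appear in device labeling, where a rate near 50% would naturally be taken as half the patients.

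**Working it through.** The documents state no expected value for endpoint 17, so there is no figure to reproduce. The check is algebra plus an illustration.

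**Inputs from the documents.** The mITT sample is 1600 with 1:1 allocation (section C.6.5.2), so 1600/2 = 800 per arm. Section C.6.6 allows up to 6% missing primary data at 24 months. No 30-day figure is given, so 6% serves only as an upper bound.

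**Assumptions.** The share of subjects affected (10%, 30%, 50%), the share unevaluated (1%, 3%, 6%) and the events per affected subject (1 to 3.5) are not in the documents.

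**Step 1: the denominator rule alone, counting each affected subject once.** Let u be the share unevaluated, p the risk in evaluated subjects, q the risk in unevaluated subjects, and c the share of affected unevaluated subjects whose event is captured.

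- True risk: R = p(1−u) + qu
- Plan's rule: E = [p(1−u) + quc] / [(1−u) + quc]
- E exceeds R when qc(1−R) > (1−u)(q−p). If q = p, this holds for any c above zero.

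With q = p and c = 1, E − R in percentage points is:

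| Unevaluated | p = 10% | p = 30% | p = 50% |
|---|---|---|---|
| 1% | +0.09 | +0.21 | +0.25 |
| 3% | +0.28 | +0.64 | +0.76 |
| 6% | +0.57 | +1.32 | +1.55 |

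**Step 2: can the direction reverse?** Take u = 6%, p = 30%, q = 60%. Then R = 0.30 × 0.94 + 0.60 × 0.06 = 0.318.

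- c = 1: +0.78 points.
- c = 0.5: E = (0.282 + 0.018)/(0.94 + 0.018) = 0.300/0.958 = 0.3132, which is −0.48 points.
- c = 0: E = 0.300, which is −1.8 points.

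So the sign depends on how the unevaluated subjects differ and how many of their events are known.

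**Step 3: add the event count.** Take 800 subjects, 240 affected (30%) and 48 unevaluated (6%), of whom 14 are affected (30% of 48, rounded). The denominator is 752 + 14 = 766. The share of subjects affected is 240/800 = 30.0%.

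| Events per affected subject | Plan's ratio |
|---|---|
| 1 | 240/766 = 31.3% |
| 1.5 | 360/766 = 47.0% |
| 2 | 480/766 = 62.7% |
| 3.5 | 840/766 = 109.7% |

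The ratio passes 100% above 766/240 = 3.19 events per affected subject. At 1.5 events the gap is 47.0 − 30.0 = 17.0 points, of which 31.3 − 30.0 = 1.3 come from the denominator and 47.0 − 31.3 = 15.7 from counting events.

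**Step 4: time cut-offs.** The numerator stops at the 30-day visit. The denominator's add-back runs to the end of the visit window, which is day 30 + 14 = 44 (section C.4.9). A subject who missed the visit has no visit date at which the numerator can stop.

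**The case against.** The strongest reply is that the text promises event rates and never calls endpoint 17 a proportion, while endpoint 16 beside it does use that term. Events per subject is a legitimate measure of complication burden, and an arm with more complications per patient should score worse on it. This stands. The excess that comes from multiple events is a difference of measure, not a biased estimate of something the plan claimed to estimate.

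The add-back also has a purpose. Without it, subjects who had an event and died or left before the visit would vanish from the denominator. Counting anyone seen at a later visit shrinks the excluded group further. Both are fair, and they are why the denominator effect is small.

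Two stronger readings are tempting:

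- **A reader might infer that the endpoint is biased upward by tens of points.** The documents do not support that. Only the denominator rule can be called bias. It amounts to about a point, and its sign is conditional. The larger gaps need assumed numbers of events per subject, and passing 100% needs more than three.
- **A reader might infer that this formula is what stops the figure being set beside endpoint 3.** Endpoint 3 covers all MAEs and endpoint 17 only procedure-related ones, so the two would differ under any formula. Endpoint 3 also already supplies subject-level MAE incidence at 30 days, though not restricted to procedure-related events.

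Section C.6.5.2 defers further analysis detail to the SAP, whose text was not available for this check. If it already counts subjects, the protocol wording should be aligned with it.

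**Conclusion.** The point holds in a limited form. As written, endpoint 17 cannot be read as the percentage of subjects with a procedure-related MAE, and nothing in its definition caps it at 100%. That follows from the text alone.

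The outcome-dependent denominator is a second, smaller fault. It adds about 0.1 to 1.6 points at 1% to 6% unevaluated if risk is similar and all events are captured. Good capture is plausible, since section C.5.2 collects adverse events from enrollment, but it is not assured. With twice the risk and half the events missed among unevaluated subjects, the effect is about −0.5 points at 6% unevaluated and 30% risk.

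Severity is minor. Section C.6.8.1 calls the endpoint descriptive, and it is not in the hierarchy of section C.6.10. The listing in section C.6.7.2 contradicts the descriptive status. An inferential method for proportions could not properly be applied to this ratio.

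**What to change.** 1. Report, for each arm of the mITT population, the share of subjects with at least one procedure-related MAE as a Kaplan-Meier estimate at day 30 after the procedure. This uses the follow-up that each early exit contributes and replaces the visit and window cut-offs with one fixed day. It still assumes uninformative loss and cannot recover events that were never reported. State how deaths not judged procedure-related are handled.
2. If a crude proportion over all mITT subjects is preferred, note that it counts early exits without a recorded event as event-free, which lowers the figure if events were missed.
3. Show the total number of procedure-related MAEs separately, labelled as a count of events.
4. Reconcile sections C.6.7.2 and C.6.8.1 on whether the endpoint is descriptive or inferential.

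The cost is wording in the protocol and SAP and a change to one table. No new data are needed.
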